Safety is assessed by primary and secondary endpoints. Primary safety endpoints include incidence of adverse and serious adverse events. Secondary safety endpoints include incidence of specific adverse events including serious infections, infusion-related reactions, hepatotoxicity, heart failure, and cytopenias. Clinically significant changes in laboratory values, vital signs, weight, and physical examination results will also be measured.

Clinical efficacy is assessed by primary and secondary endpoints. Primary endpoints include the change from baseline in inflammatory markers (IL-6, D-dimer, C Reactive protein), time to clearing PCR test, change from baseline oxygenation, and time to return to room air (RTRA). Secondary endpoints include change from baseline of chest x-ray, change from baseline of CT scan, change from baseline of clinical laboratory values, adverse and serious adverse events, change in exploratory markers, and change in ordinal scale.

Analysis Population

Safety: All subjects receiving at least one infusion will be included for safety analysis.

Efficacy: All subjects receiving all four infusions will be included for efficacy analysis.

Additional sub-analysis will be performed comparing subjects receiving any other experimental treatment for COVID-19, to those who are not, in the following items:

- Change from baseline oxygenation
- Change from baseline chest x-ray
- Change from baseline CT scan
- Time to clearing PCR test
- Change from baseline inflammatory markers (IL-6, D-dimer, C Reactive protein)
- Change from baseline in IL-10
- Change from baseline in CD4:CD8 ratio
- Change from baseline in CD3⁺CD56⁺
- Change from baseline in VEGF
- Change from baseline in the 7-point ordinal scale

Demographic and Baseline Characteristics

Information describing subjects' gender, race/ethnicity, and age will be displayed in tables similar to the ones included below. The number and percent of the total sample population will be calculated for each demographic category.

Demographics	Female		Male		Both Genders	
Race/Ethnicity	N	%	N	%	Total	%
White						
Black or African American						
Hispanic or Latino						
Other (Specify)						
Total						

The mean, minimum, and maximum age at enrollment will be determined using standard calculations. The number and percent of total subjects in each age group will be calculated and reported.

Age at Enrollment	N	%
Mean		
Minimum		
Maximum		
	N	%
≥ 18 years		
18-21 years		
22-29 years		
30-39 years		

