## 4. ANALYSIS POPULATIONS

Population	Definition / Criteria	Analyses Evaluated
Safety analysis set	

• All randomised subjects who received at least one dose of HB-adMSCs infusion or placebo.

• If participants receive a treatment different to their randomized treatment, they will be analysed according to the treatment actually received.

	

• Safety

• Study Population

Efficacy analysis set	

• All randomized participants who received all 4 infusions of HB-adMSCs or placebo.

• Participants will be analysed according to their randomized treatment.

	

• Efficacy

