The Bayesian approach addresses these questions: (1) “Among patients with suspected COVID-19, what is the probability that allogeneic HB-adMSC 100mm confers benefit relative to placebo on status on inflammatory markers (C-Reactive protein, TNF-alpha, IL-6, IL-10), change from baseline oxygenation, and time to return to room air (RTRA) at treatment Day 10?” (2) “What is the best estimate of these effects?” and (3) “What is their precision?” By estimating the probability that such effects exist, we are assessing the probability that the alternative hypothesis is true; a probability that is, by definition, not accessible to Frequentist methods. The FDA has discussed the use of Bayesian statistical methods to make decisions regarding the efficacy of new treatments as an alternative to Frequentist methods in developing clinical applications. The current proposal will provide the optimal, unbiased estimates for the benefit conferred by allogeneic HB-adMSC, while also estimating the probability that such effects exist. Posterior distributions can then be used as informative priors for continued monitoring in expansions of treatments and treatment strategies exhibiting initial promise.

Presentation of results from the statistical models will include the estimated conditional/marginal mean treatment effects. For all endpoints analysed statistically, estimated mean treatment differences will be presented together with 95% credible intervals and posterior probabilities,

HB-adMSCs 100MM vs Placebo

All safety evaluations will be presented using Safety Analysis Set. The efficacy analysis will be presented using Efficacy analysis set.

Individual safety and efficacy parameters will be listed.

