#### 7.1.3. Population of Interest

The primary efficacy analyses will be based on the efficacy analysis set population, unless otherwise specified.

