#### **7.1.4.1. Statistical Methodology Specification**

Initial analyses examining group differences for baseline variables will use cross-tabulation, ANOVAs, and examination of correlations between baseline variables and specified outcomes. For the purposes of evaluating the comparability of groups, a posterior probability of  $\geq 75\%$  will constitute evidence for statistically reliable differences. Baseline or demographic variables on which group differences are detected, and which are correlated with outcomes, meet the definition of confounders and will result in two sets of analyses: one in which only the stratification variables are included as covariates, and another where the relevant variable is included as a covariate. This will permit determination of the degree to which any group differences might confound conclusions regarding treatment. A third set of analyses will model the effect of treatment group (controlling for stratification variables) on each outcome, focusing on the subgroup of patients who survived through the last infusion visit where statistically feasible.

Broadly, the data analytic strategy will use generalized linear, multilevel, and survival/cox proportional hazard models (R v 4.1, 2021; brms v 2.17; RStan v 2.21) for discrete, continuous, and time-to-event outcomes. Multilevel generalized linear modeling to account for clustering of patients within site and repeated observations within patients will evaluate continuous, dichotomous, and count data. All analyses will address potential missingness through joint modeling of observed outcomes and the missing data, an approach robust to ignorable missingness (i.e., MCAR and MAR). Sensitivity analyses will evaluate robustness of analytic conclusions to missing data. Non-ignorable missing data patterns will be addressed through pattern-mixture modeling methods.

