### 7.2.4.1. Statistical Methodology Specification

Principles will follow the same procedures as the Primary Efficacy analyses (see 7.1.4.1). Three sets of analyses will be performed: the first adjusting for stratification variables, a second set adjusting for variables found to be confounding (see 7.1.4.1), and a third set focusing on the subgroup of surviving patients as of the last infusion where statistically feasible. Bayesian generalized multilevel models will evaluate the differential trajectories of each secondary endpoint as a function of treatment, time, and the interaction of treatment and time.

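### As written, the survivors-only third set of efficacy analyses refits the first set, and no specified efficacy analysis includes patients who die before infusion 4

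*SAP*

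**What the plan says.** SAP section 4 defines the efficacy analysis set as "All randomized participants who received all 4 infusions of HB-adMSCs or placebo", analysed by randomised arm. The protocol agrees, under Analysis Population in its Statistical Analysis section: "All subjects receiving all four infusions will be included for efficacy analysis". SAP 7.1.3 sets the default: "The primary efficacy analyses will be based on the efficacy analysis set population, unless otherwise specified". SAP 7.2.3 does the same for secondary endpoints, and SAP 5.7 states without exception that "The efficacy analysis will be presented using Efficacy analysis set".

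SAP 7.1.4.1 then describes three sets of analyses, called sets 1, 2 and 3 here.

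- Set 1 is "one in which only the stratification variables are included as covariates".
- Set 2 adds any baseline variable found to be a confounder.
- Set 3 again adjusts for the stratification variables, and is run in a restricted population: "focusing on the subgroup of patients who survived through the last infusion visit where statistically feasible".

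SAP 7.2.4.1 carries the scheme over to secondary endpoints, with "a third set focusing on the subgroup of surviving patients as of the last infusion where statistically feasible".

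The last infusion visit is Visit 5, infusion 4, Day 10 (SAP 2.2 and 7.1.4.2; protocol Table 2).

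**The concern.** A survivors-only analysis is informative only beside one that contains the deaths. Here the comparator, set 1, is already restricted to people who lived to receive infusion 4, so the survivor restriction appears to have nothing to remove.

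Two things are at stake. First, the report would show a main analysis and a survivor analysis that agree, and that agreement would be guaranteed by the definitions. Second, the gap that a reader might expect set 3 to address would stay open. Patients who die before infusion 4 have the worst outcome on the trial's own ordinal scale (level 1), yet they enter no specified comparison of markers, oxygenation or return to room air.

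**Working it through.** **Inputs.** The efficacy set definition (SAP section 4); the default populations (SAP 5.7, 7.1.3, 7.2.3); the covariates and population of sets 1 and 3 (SAP 7.1.4.1, 7.2.4.1); the visits in the primary model, Visits 2 to 5 (SAP 7.1.4.2); the planned 100 patients, 60 and 40 by arm (protocol Investigational Plan), consistent with 3:2 allocation (SAP 2.2). The plan states no figure to reproduce.

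**Step 1: patients.** Let E be the randomised patients who received infusions 1 to 4, and S those alive through the last infusion visit. Receiving infusion 4 requires being alive at that visit, so E is contained in S and E ∩ S = E. The one exception is a death during the infusion 4 visit after the infusion was received.

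**Step 2: covariates and model.** Sets 1 and 3 both adjust for the stratification variables only. No different model, prior or time span is named for set 3. With the same patients, covariates and model, the estimate is the same, and a Bayesian refit differs only by Monte Carlo error. Set 3 duplicates set 1, not the confounder-adjusted set 2.

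**Step 3: which endpoints.** The identity covers the primary endpoints and the secondary endpoints analysed in the efficacy set. It is not established for AEs and SAEs. SAP 7.2.1 lists these as secondary endpoints, so 7.2.3 points to the efficacy set. SAP sections 4 and 8 assign safety to everyone with at least one infusion. In that larger set, survivors are a true subset whenever someone dies earlier.

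**Step 4: who is in no set.** With N = 100 and an assumed proportion p dying before infusion 4, the number outside all three sets is N × p:

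- p = 5%: 100 × 0.05 = 5
- p = 10%: 100 × 0.10 = 10
- p = 20%: 100 × 0.20 = 20

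The documents give no death rate. The identity in steps 1 and 2 does not depend on one.

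**Step 5: the alternative parent population.** Suppose set 3 were drawn from all randomised patients instead. A simulation (60:40 patients, 4,000 replicates per scenario) shows the sizes. Death before infusion 4 was assumed at 5% or 15% for a patient of average severity, with higher risk in sicker patients. Either 0% or 10% of living patients missed an infusion.

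| Death, active / placebo | Missed infusion | Mean efficacy set | Mean survivors, all randomised | Mean deaths |
|---|---|---|---|---|
| 5% / 5% | 0% | 92.7 | 92.7 | 7.3 |
| 5% / 5% | 10% | 83.5 | 92.7 | 7.3 |
| 5% / 15% | 0% | 88.1 | 88.1 | 11.9 |
| 5% / 15% | 10% | 79.3 | 88.1 | 11.9 |
| 15% / 5% | 10% | 77.2 | 85.7 | 14.3 |

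Within the efficacy set, the survivor subgroup equalled the whole set in every replicate and the estimates differed by exactly 0. That only restates step 1. The useful result is the other comparison: all-randomised survivors exceed the efficacy set only by living patients who missed an infusion. The 7.3 to 14.3 deaths per 100 are in neither set.

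**The case against.** **The parent population is not stated.** SAP 7.1.3 and 7.2.3 allow exceptions to their default, and 7.1.4.1 does not say that the survivors are a subgroup of the efficacy set. A survivor restriction makes sense only if its authors expected deaths in the other sets, so they may have had a wider population in mind. The references to planned displays are broken and cannot settle it. This stands as an ambiguity but does not rescue set 3. Section 4 defines no other efficacy population, none is named for set 3, and 5.7 makes no exception. Survivors among all randomised patients would still exclude every earlier death, and would compare arms after selecting on an outcome that treatment could affect.

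**The harm is not documented.** A reader might infer that the SAP offers set 3 as proof of robustness to mortality, and so gives false reassurance. The documents do not support that. SAP 7.1.4.1 gives a purpose only for the comparison of sets 1 and 2 (confounding) and none for set 3. A redundant analysis does not bias the primary estimate. What can be said is that agreement with set 1 would carry no information about deaths, however it is reported.

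**Deaths are not invisible.** This is right. Fatal events are SAEs and enter safety reporting for anyone with at least one infusion. Deaths after infusion 4 can enter the ordinal scale, which is modelled through Visit 6. The gap is limited to efficacy comparisons and to deaths before infusion 4.

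**The cause lies elsewhere.** Also right: the four-infusion rule removes these patients, and deleting set 3 alone would restore none of them. Any replacement must therefore name its population. Under the 7.1.3 default, an endpoint that counts death as failure would be just as empty.

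**Missing-data methods might cover the gap.** SAP 7.1.4.1 plans joint modelling and pattern-mixture analyses, but does not say that they reach beyond the efficacy set.

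**Conclusion.** The point holds for the primary endpoints and the non-safety secondary endpoints. As written, set 3 is set 1 refitted and adds no information: the difference is zero except for Monte Carlo error or a death during the infusion 4 visit. This rests on reading set 3 under the SAP's stated default population, the only efficacy population defined. On the wider reading the two sets would differ, but only by living patients who missed an infusion.

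The practical consequence is that no specified efficacy analysis shows what deaths before infusion 4 do to the result. How many patients that concerns is unknown; the 5, 10 or 20 per 100 above are assumptions. The documents do not support a claim that the SAP presents set 3 as evidence on mortality, or that deaths go unreported. The change should be made, and it is a modest one.

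**What to change.** In SAP 7.1.4.1 and 7.2.4.1, replace set 3 with a sensitivity analysis in **all randomised patients**, analysed as randomised. State it in 7.1.3 and 7.2.3 as an exception to the efficacy-set default. Specify:

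- **Room air:** alive and on room air at Day 10, compared between arms, with death counted as failure.
- **Oxygen saturation, CRP and IL-6:** a rank analysis by arm, with death before Day 10 as the worst rank. The protocol's Efficacy Analysis section gives the beneficial direction for these.
- **IL-10 and TNF-alpha:** state the beneficial direction first, or omit the ranking. Neither document gives one.
- **Survivors-only table, if kept:** name its parent population and label it descriptive.

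The cost is SAP wording, in a document still marked as draft, plus one re-specified sensitivity analysis. The data are already planned: fatal SAEs are collected through Day 28, room-air status is an endpoint, and patients who stop infusions but keep consent are followed to Day 28. The downside is slightly more analysis work, and ranked results are not in marker units.

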### 5.3.1. Change from Baseline

Definition	Reporting Details
Change from Baseline	= Post-Dose Visit Value – Baseline
% Change from Baseline	= $100 \times [(Post-Dose Visit Value – Baseline) / Baseline]$

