## **5.4. Examination of Covariates, Other Strata and Subgroups**

### **5.4.1. Covariates and Other Strata**

Baseline will be included as a covariate in the efficacy analyses, wherever applicable. Stratification variables used at randomization (site, illness severity, pre-existing condition, ethnicity, age group) will be included as covariates.

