## **5.5. Multiple Comparisons and Multiplicity**

In keeping with sound Bayesian analytic principles, salient error rates/operating characteristics for confirmatory analyses in each component of the trial (provided in the sample size justification section) result from Monte Carlo simulation. Any secondary analyses for which issues of multiplicity might be a consideration will use weakly, informative priors to regularize all estimates. Means for these regularizing priors will be centered on the null hypothesis, with variances determined by the scale of the data and credible effects previously reported in the literature in the most closely analogous studies. Of note is the principle that the more informative the priors are (based on credible estimates of these effects), (1) the greater the degree of regularization, (2) the more conservative the estimates, and (3) the more likely the results are replicate outside of the current sample. Indeed for any observed results, the Bayesian approach makes it possible to determine the sensitivity of the results to prior assumptions; the degree of prior skepticism an observer would require before dismissing the estimated treatment effect. In the interest of transparency and reproducibility, the resulting reports will provide the specifications of Bayesian model priors used for all secondary analyses.

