## 7. EFFICACY ANALYSES

### 7.1. Primary Efficacy Analyses

#### 7.1.1. Endpoint / Variables

The primary efficacy endpoints are changes from baseline in the following outcomes at each post-baseline visit:

- Inflammatory markers (TNF-alpha, IL-10, IL-6, C-Reactive protein)
- Oxygenation
- Time to return to room air (RTRA) and proportion of patients with room air status

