Evaluation of posterior distributions will permit statements regarding the probability that effects of varying magnitudes exist, given the data. Specification of diffuse, neutral priors will reflect the initial uncertainty regarding effect sizes. For all generalized linear models, priors for regression coefficients will be specified as  $\sim$ Normal ( $\mu=0$ ,  $\sigma^2=1 \times 10$ ), and priors for the levels one and two error variances will be specified as  $\sim$ Half-Normal ( $\mu=0$ ,  $\sigma^2=1 \times 10^3$ ). The choice of prior distribution for level two variances will follow Gelman's recommendations from the literature. Priors for the comparison of proportions will be specified as  $\sim$ Beta ( $\alpha=1.0$ ,  $\beta=1.0$ ).

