#### **7.1.4.2. Data Analytic Models**

All primary endpoint efficacy measurements available at post-baseline at scheduled measurements (Visits 2 through 5 [infusions 1 through 4] for inflammatory markers, oxygenation, and room air status) will be analysed in a generalized linear mixed model. The model will predict each outcome as a function of the interaction between the fixed factors treatment group and time, controlling for lower order effects of time and treatment group. Models will control for stratification variables (see [Covariates and Other Strata](#)), and subject will be included as random effects.

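### The primary marker models use one fixed coefficient prior with no stated outcome scale, so on raw units its strength depends on the laboratory unit

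*SAP*

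**What the plan says.** SAP 7.1.4.1 describes the primary priors in these terms: "Specification of diffuse, neutral priors will reflect the initial uncertainty regarding effect sizes". It continues: "For all generalized linear models, priors for regression coefficients will be specified as" a Normal distribution with mean 0 and variance printed as 1 x 10. In the same sentence, "priors for the levels one and two error variances will be specified as" Half-Normal with 1 x 10^3.

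The four inflammatory markers are primary endpoints. SAP 7.1.1 states: "The primary efficacy endpoints are changes from baseline in the following outcomes at each post-baseline visit". SAP 5.3.1 defines the change as "Post-Dose Visit Value – Baseline", a raw difference, and also defines a percentage change without saying which one is modelled. SAP 7.1.4.2 uses a generalized linear mixed model: "The model will predict each outcome as a function of the interaction between the fixed factors treatment group and time". It lists Visits 2 to 5, and Visit 2 is Day 0, so visit values may be modelled instead of changes. SAP 5.4.1 adds: "Baseline will be included as a covariate in the efficacy analyses, wherever applicable".

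Neither document gives a unit, family, link, transformation or standardisation for these markers. The one rule that ties prior width to the data is in SAP 5.5, "with variances determined by the scale of the data and credible effects previously reported in the literature", and it covers secondary analyses only. Under SAP 5.7 the results are mean treatment differences with credible intervals and posterior probabilities.

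**The concern.** A prior width is a number of outcome units. A variance of 10 puts about 95% of the prior mass within 1.96 x 3.16 = 6.2 units of zero. Whether that is diffuse depends on how large a typical marker difference is in the unit used, and the plan does not state the unit. The same patients, with CRP recorded in a unit ten times smaller, give numbers ten times larger and a prior that is 100 times tighter relative to the variance of the data.

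Inference is primarily Bayesian (SAP 2.4 and 5.7), so the posterior probability of benefit at Day 10 is the main result for each marker. If the prior is tight, that probability moves towards one half and the estimate towards zero, for reasons unrelated to the patients. The plan commits to no prior-sensitivity run for the primary models. The sensitivity analyses in SAP 7.1.4.1 concern missing data, and SAP 5.5 says only that sensitivity to the prior can be determined.

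**Working it through.** The plan contains no figure to reproduce. The protocol bases the sample size on anticipated demand and gives no SD, effect size or power.

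**Inputs.** Arms of 60 and 40 (protocol, Investigational Plan). Prior variance V = 10 as printed, or 1,000 if an exponent was lost. The SD of change, in raw units, is an assumption throughout.

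**Step 1: one visit, two arms.** SE = SD x sqrt(1/60 + 1/40) = 0.2041 x SD. Weight on the data: w = V/(V + SE^2). Posterior mean = w x observed difference. P(benefit) = Phi(z x sqrt(w)).

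Take an observed difference of 0.5 SD, so z = 0.5/0.2041 = 2.449 and a flat prior gives 0.993. Express the same data in two units ten-fold apart, with V = 10:
- SD 5: SE 1.021, w = 10/(10 + 1.042) = 0.906. The difference of 2.5 becomes 2.26, and P(benefit) is 0.990.
- SD 50: SE 10.21, w = 10/(10 + 104.2) = 0.088. The difference of 25 becomes 2.19, and P(benefit) is 0.766.

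With V = 1,000 the weights are 0.999 and 0.906.

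**Step 2: the repeated-measures model of SAP 7.1.4.2.** The terms are treatment, categorical time, their interaction and a random intercept. The posterior mean is (X'S^-1 X + D)^-1 X'S^-1 y, where S is the within-patient covariance and D has 1/V for each coefficient and 0 for the intercept. Changes are taken at days 3, 7 and 10, or visit values at days 0, 3, 7 and 10 with the change contrast read off. Within-patient correlation is 0.3 to 0.7, the effect is constant or grows linearly, and arms are coded 0/1 or symmetrically. SD is the SD of change in both cases. Share of a Day 10 effect kept:

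| Assumed SD | V = 10, changes | V = 10, visit values | V = 10^3, changes | V = 10^3, visit values |
|---|---|---|---|---|
| 4 | 96-98% | 89-92% | about 100% | about 100% |
| 8 | 85-92% | 68-76% | about 100% | over 99% |
| 20 | 48-61% | 29-46% | about 99% | 97-98% |
| 80 | 6-11% | 3-9% | 85-92% | 68-76% |

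The share depends only on SD^2/V. As a check, 80^2/1,000 = 6.4 = 8^2/10, and the matching cells agree. The loss reaches 10% at these SDs:
- V = 10: about 6-9 units for changes, about 4 for visit values.
- V = 10^3: about 62-88 units for changes, about 40 for visit values.

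Adding baseline and stratum covariates changes little (V = 10, changes: 82-91%, 45-60% and 6-11% at SD 8, 20 and 80). So does 51/34, that is 15% dropout (82-90%, 44-57% and 5-10%, with 0/1 coding).

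**Step 3: same data, two units, variances estimated.** There were 81 simulated data sets with a true effect of 0.5 SD, baseline and strata in the model, and V = 10. At SD 50 the mean estimate is 0.10-0.12 SD and the median P(benefit) 0.91-0.94. Divided by 10, they are 0.46 SD and about 0.995. At V = 10^3 both units give 0.46-0.48 SD and 0.995-0.997. P(benefit) at SD 50 is higher than in step 1 because this model uses repeated visits and baseline adjustment. The direction is the same.

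**Step 4: arm coding.** With changes modelled, V = 10, SD 20 and the active arm coded 1, a fall of 1 SD shared by both arms leaks 0.11 SD into the treatment contrast. Symmetric coding leaks at most 0.02.

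**Step 5: other scales.** With SD near 1 (standardised, or roughly so on a log scale), w = 10/(10 + 0.0417) = 0.996 and the prior is weak. For percentage change the laboratory unit cancels, but the prior SD is then 3.16 percentage points, which would be tight.

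**The case against.** The strongest reply is that the variance of 10 is probably a misprint. Writing ten as 1 x 10 is odd, the same sentence prints 10^3 for the Half-Normal, SAP 7.2.4.1 prints 10^3 for the secondary intercepts, and the prior is called diffuse. At 10^3 most of the problem goes. This stands as a real possibility that the documents cannot settle. Even then the unit dependence is not zero: with visit values, 12-16% is lost at SD 50.

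Second, the size rests on assumed SDs and on model details the plan leaves open. That is correct. If time were linear in days with a linearly growing effect, 83-85% would be kept at SD 80 even with variance 10, although treating time as a fixed factor points to categorical time.

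Third, silence should not be read as raw units. This also stands: percentage change is defined in SAP 5.3.1, and a log scale or log link would make the treatment coefficient unit-free. The claim is therefore conditional.

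Fourth, shrinkage to zero is conservative, unadjusted means are reported alongside (SAP 7.1.2), and supplementary frequentist analyses are allowed (SAP 2.4). The means would expose a heavily shrunken estimate, but they do not supply the posterior probability. Nor is conservatism what the plan promises: it keeps sceptical priors for subgroups and calls the primary priors neutral. Shrinkage would mute harm as much as benefit, and SAP 5.7 names worse marker status as an open question.

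**Conclusion.** The point holds in conditional form and should be fixed. The plan labels a fixed-width prior diffuse without stating the scale on which it acts. On raw units with an identity link, the posterior probability and estimate for each marker then depend on the laboratory unit. The effect ranges from negligible (SD of a few units, or variance 10^3 at moderate SDs) to dominant (variance 10 at SD 20 or more). It rests on assumed SDs, categorical time and the 60/40 split.

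A reader might infer that the primary prior is wrong, or that it will overwhelm the data. The documents do not show this: the outcome scale and the intended variance are both unsettled, and on a standardised or log scale the printed prior is harmless. A reader might also infer that a trial decision would flip. The SAP states no threshold for the primary posterior probabilities, so no stated decision is at risk. Room-air status and time to return to room air are not affected, and oxygenation only slightly. Placing the Half-Normal on error variances is a wording matter: read on the standard deviation, it causes no difficulty.

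**What to change.** 1. Confirm the coefficient prior variance, and that the code enters it as intended (variance or SD).
2. Name the outcome scale (value, change or percentage change), unit and link for each marker.
3. Divide each marker outcome by its pooled baseline SD over both arms before fitting, or set the prior SD to 3.16 times that SD, and back-transform effects to the original unit. The SD of change is sqrt(2(1 - r)) times the baseline SD, which is 1.18 to 0.77 for correlation r of 0.3 to 0.7. With changes modelled, the printed prior then keeps at least 99% of the effect, and at least 97% even if the ratio is three. This works whichever exponent was meant.
4. State the time coding and use symmetric arm coding.
5. Add one wider-prior sensitivity run for the primary marker models.

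The same scaling for oxygenation is optional, and the Half-Normal needs at most a clarifying word.

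The cost is SAP wording, a few lines of code and one extra model run per marker. No new data are needed, and effects are still reported in their original units. The downside is that a prior stated on a standardised scale is less direct to read clinically.
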